9.4. Randomisation

Once all eligibility data and immunophenotyping results are available, randomisation will be performed centrally by CTU staff following confirmation of eligibility from study site personnel, using the OCTRU randomisation system. Patients will be randomised in a 1:1 allocation ratio to either TNF or IL-17A inhibitors and these drugs will be prescribed open label as in routine care. The randomisation will use a minimisation algorithm to ensure balanced allocation across the treatment groups, stratified by activated Th17 proportion (\leq />1.58%), psoriasis severity (PASI < or \geq 10) and study centre. The minimisation algorithm will include a probabilistic element and a small number of participants randomised by simple randomisation at the start of the trial to seed the algorithm in order to ensure the unpredictability of treatment allocation. Patients will be contacted by telephone to confirm continued consent to participate and to advise them of their treatment allocation.

There is no blinding of therapy allocation so no allocation code or code-breaking procedure is required. All relevant study personnel will be informed of the treatment allocation by email.

Following randomisation the GP letter must be sent by the site team to the participant's GP to notify them of study participation and treatment allocation.

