9.9. Sample Handling

9.9.1 Sample handling for study purposes

Fresh peripheral blood samples (80 ml) will be collected from all participants at screening, and additionally from ~100 participants attending the 3 hub sites (Oxford University Hospital, Glasgow Royal Infirmary, Guy's and St Thomas' NFT London) at 4 weeks and 24 weeks for analysis.

These blood samples will be transported to one of the three laboratory centres (University of Oxford, University of Glasgow, King's College London [all UK]) for processing. Samples need to arrive at the laboratory within the time specified in the OPTIMISE Sample Handling Manual. See sample handling manual for further details.

Samples will be used for a number of analyses that will be undertaken at different times in the study including eight colour flow cytometry. Samples will be split into individual aliquots for different purposes, with these aliquots being distributed to and then used/stored at all three of the laboratory centres. All sample handling will be performed following trial-specific standard operating procedures. Antibodies used and flow cytometer optimisation will be standardised across the sites to ensure consistent results.

To obtain the immunophenotyping results required for randomisation, activated Th17 cells will be identified based on CCR6 and CXCR3 expression on CD4 T cells and co-expression of known T cell activation markers CD38 and HLA-DR, as described in the Miyagawa study¹³. This activated Th17 proportion (\leq />1.58%) from baseline samples will be included in the randomisation process to ensure equal stratification across the RCT arms.

In parallel, we will perform intracellular cytokine staining of IL-17A/F and interferon gamma in CD4, CD8 and MAIT cells to further elucidate the mechanisms of disease.

Aliquots of the research blood samples will be stored frozen at the three lab centres for subsequent indepth transcriptomic interrogation on whole blood baseline samples to identify additional predictors of response. Using predefined machine learning techniques that generated predictive signatures in ORBIT [21] these data will be incorporated in the second and third stage analysis detailed below. On a subset of samples (20 high Th17 and 20 low Th17) we will also perform cell sorting and RNA sequencing on OPTIMISE_Protocol_V5.0_17Jun2022.docx

Clinical Research Protocol Template version 15.0

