© Copyright: The University of Oxford and Oxford University Hospitals NHS Foundation Trust 2019

Page 25 of 43

isolated CD4, CD8, CD14 and NK cells in order to understand the cell-specific transcriptional predictors of response and refractory disease. Processing of samples for RNA sequencing and/or RNA sequencing may be undertaken at the laboratory centres or may be outsourced to external service providers under appropriate contracts. We will use the immune subset-specific transcriptomic data to de-convolute the whole blood RNA sequencing samples from the whole cohort using bioinformatic approaches [31].

The same analysis will be repeated at 4 weeks and 24 weeks on patients recruited from the 3 hub sites ($n\approx100$) to examine the effect of therapy and relate this to clinical response. Samples collected will be prepared and frozen for analysis.

Samples may also be stored long term for analysis outside of this study. Consent (optional) will be sought from all participants for long term storage and future use of samples. Any sample destruction will be done in with HTA requirements.

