In phase 2, additional hypothesis generating analyses will be undertaken to investigate alternative potential models for predicting response to different classes of biologic. This large dataset will be used to model response rates adjusting for other variables (for example: different therapies (TNFi vs IL-17i), standard care (the therapy originally planned by the recruiting physician), alternate cut-off points of Th17 proportions, Th17 proportions as a continuous measure or alternative laboratory measures of immunophenotype including transcriptomics. We will be able to use the models developed to predict what outcomes would be expected from a precision medicine based clinical pathway. This could then be validated in a future study.

In phase 3, we will use the immunophenotyping and transcriptomic data generated to gain mechanistic insight into genes and pathways that underpin the clinical response. Analysis of paired flow cytometry samples before and after treatment in each arm will allow us to understand the stability of the Th17 compartment in MDA responders and non-responders. This question is especially pertinent in view of data suggesting the intracellular IL-17A signature increases after treatment with TNF blockade [25, 43]. Similarly, we will use the RNA sequencing data to look at immune subset-specific differential gene expression from Th17-high, anti-IL-17A responders and refractory patients and TH17-low anti-TNF responders and refractory patients. Genes identified will be validated in the whole blood RNA sequencing data-set and we will use network and pathway analysis to identify key nodes of refractory disease which can be validated in future mechanistic studies.

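### Genes discovered in 40 sorted-cell participants are to be validated in whole-blood data from the whole cohort, which still contains those 40, so the validation is not independent

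*Protocol*

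**What the plan says.** Section 9.9.1 defines the discovery material: "On a subset of samples (20 high Th17 and 20 low Th17) we will also perform cell sorting and RNA sequencing" of isolated CD4, CD8, CD14 and NK cells. These are trial participants, not an outside sample.

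The same section says the cell-specific data will be used to "de-convolute the whole blood RNA sequencing samples from the whole cohort". The whole-blood set is thus the entire trial population, including the 40.

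Section 11.2 (phase 3) describes the discovery contrasts as "Th17-high, anti-IL-17A responders and refractory patients and TH17-low anti-TNF responders and refractory patients", and then states: "Genes identified will be validated in the whole blood RNA sequencing data-set".

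The secondary objectives (Synopsis and section 6) include finding a limited number of transcriptomic biomarkers that can be validated in whole blood. Only the key nodes from the network and pathway analysis are referred to future mechanistic studies for validation; the genes are to be validated inside this trial. No section says that the 40 leave the whole-blood set at that step.

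**The concern.** A gene picked because it separates responders from refractory patients in a small group carries that group's chance differences. If the same patients reappear in the validation data with the same week-24 outcome, part of that chance difference reappears too, to the extent that sorted-cell and whole-blood expression are correlated. Null genes then pass validation more often than the nominal rate, and the result looks like a replication when part of it is the discovery data seen again.

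This bears on a stated secondary objective and on which genes are carried into later studies. It is not a matter of detail that is simply absent: the protocol itself names the data set that validates the genes, and describes it in a way that includes the discovery participants.

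**Working it through.** **1. The protocol's own figures.** 424/4 = 106 per Th17-by-treatment cell, as section 11.3 states. The power table uses 388, so 388/4 = 97 per cell. A Wald test of the logistic interaction at 97 per cell (0.4/0.6 v 0.6/0.4) gives 97.5% by formula and 97.7% by simulation, against the stated 98.06%. The cell sizes used below are therefore the protocol's own. It gives no group sizes, thresholds or error rates for phase 3, so there is no stated figure to reproduce there.

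**2. Size of the overlap.**
- Whole cohort: 40/424 = 9.4%.
- One contrast cell, if about 10 of the 40 fall in it: 10/106 = 9.4%.
- One contrast cell, if all 40 lie in the two named contrasts, 20 in each: 20/106 = 18.9%.

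**3. Effect on null genes.** Assumptions not in the protocol: discovery at two-sided p<0.001; validation counted when two-sided p<0.05 in the same direction; correlation ρ between a person's sorted-cell and whole-blood value of 0.3, 0.5 or 0.7; two-sample t-tests on normal values. De-convolution is not modelled.

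For each null gene, discovery values D are standard normal in both response groups. Selected genes are retested in whole blood. Overlapping participants have W = ρD + √(1−ρ²)·ε; all others have independent standard normal values. With no overlap, the expected rate is 0.05/2 = 2.5%.

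A 97-person cell at the assumed 60% response is 97 × 0.6 ≈ 58 responders v 39 refractory. All 388 at the overall 50% is 194 v 194. Ranges span separate simulation runs with different numbers of selected genes.

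| Discovery | Validation set | ρ = 0.3 | ρ = 0.5 | ρ = 0.7 |
|---|---|---|---|---|
| 6 v 4 | 97-person cell | 4.3–4.8% | 5.6–5.9% | 7.8–8.7% |
| 6 v 4 | all 388 | 3.2–3.4% | 3.6–4.0% | 4.3–4.4% |
| 10 v 10 | 97-person cell | 5.0–6.3% | 9.6–11.4% | 15.8–18.7% |
| 10 v 10 | all 388 | 4.2% | 5.2% | 6.5% |
| either, overlap removed | either | about 2.5% | about 2.5% | about 2.5% |

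The 6 v 4 rows come from runs with about 2,000 to 8,300 selected genes. In the third row, 5.0, 11.4 and 18.7% come from a run with only about 400 selected genes, where the standard error at 18.7% is √(0.187 × 0.813/400) ≈ 1.9 points; runs with about 2,000 and 8,400 genes gave about 6–16%. At ρ = 0 the overlap does no harm (about 2.2–2.7%).

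The two discovery sizes are illustrations. 6 v 4 follows from 20 × 0.5 = 10 on the named drug at 60% response; 10 v 10 follows if the 40 are chosen evenly from the four response groups in section 11.2.

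**4. After exclusion.** 424 − 40 = 384 overall. Per contrast cell, before losses to follow-up: 106 − 10 = 96, or 106 − 20 = 86 if all 40 lie in the two named contrasts.

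**The case against.** The strongest reply has three parts.

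First, validation may be meant loosely: checking that a cell-specific signal can be seen in an accessible sample. Phase 2 is called hypothesis generating, phase 3 is mechanistic, and no trial decision or controlled error rate depends on this step. That stands as a limit on importance. It does not make the step independent, and the text does not restrict the word to detectability.

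Second, the statistical analysis plan, which was not available, may define the validation set. It may, and if it already excludes the 40 the matter is closed. But the protocol fixes which data set is used and describes it as the whole cohort, so the protocol wording needs the qualification in any case.

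Third, the inflation depends on an assumed correlation and threshold, and is small if all 388 are used. This also stands, and is why a range is given.

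A reader might go further and infer that the 40 are picked by Th17 level alone, so that, with 1:1 allocation, only about 6 responders v 4 refractory patients remain per contrast and half of the sorted samples are wasted. The documents do not support this. Section 9.9.1 gives the composition of the subset (20 high, 20 low), not a rule that it is drawn regardless of drug or response. The same section gives its purpose as predictors of response and refractory disease, and section 11.2 names the four response groups. Selection by drug and response is compatible with the text. Samples outside the two contrasts would also still serve the de-convolution.

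Nor should outcome-based selection be pressed as an evident improvement. Taking only Th17-high participants on IL-17A inhibitor and Th17-low participants on TNF inhibitor confounds drug with Th17 level in the sorted data. It may also need cells frozen in a form that the protocol does not clearly provide, since its sentence on frozen aliquots concerns whole-blood baseline samples.

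**Conclusion.** The point holds as a limited one: as written, discovery participants are part of the validation set, so the gene validation is not independent. This follows from sections 9.9.1 and 11.2 however the 40 are chosen.

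The size is modest. Under the assumptions above, a null gene validates about two to three times as often as it should in a 97-person cell with 6 v 4 discovery, and less than twice as often in all 388. The effect is larger with 10 v 10 discovery tested in the contrast cell, because the overlap there is about twice as large. Using the sorted-cell data to de-convolute the whole-blood data may add a second dependence; it was not quantified.

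This is a cheap improvement to a mechanistic analysis. It does not touch the primary interaction test.

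**What to change.** State in section 11.2 that the 40 sorted-cell participants are excluded from the whole-blood set used to validate genes found in the sorted cells. The full-cohort result may be shown beside it, labelled as a secondary description and not as validation.

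The cost is wording plus about 9% of the validation participants: up to 384 remain, so standard errors widen by √(424/384) = 1.05, about 5%. Within a contrast cell about 96 of 106 remain if about 10 are removed, or 86 if 20 are removed (√(106/86) = 1.11, about 11% wider). No sample, assay or visit changes.

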11.3. Sample Size Determination

This study has been powered to test for a biomarker-treatment interaction in response as defined by achievement of the MDA criteria at 24 weeks. Based on RCT and registry data for both drugs $^{10\,24\,25}$, we expect similar non-biomarker stratified MDA response rates in each treatment arm in the RCT and estimate the MDA response rate overall to be ~50%.

A total of 424 participants will be randomised. Based on 10,000 simulations, this study sample size has 98% power and 5% (2-sided) significance to detect a biomarker-treatment interaction. This assumes the proportion of MDA responders is 60% and 40% for participants with low/high Th17 treated with TNFi, and 40% and 60% for participants with low/high Th17 treated with IL-17Ai. This equates to a relative interaction effect of 0.2. A further assumption is that the baseline activated Th17 levels (high versus low) will be split 50:50. Using the same design and methodology as the Japanese study, we have refined the cut-off point proposed for this study. The cut point has been set as the median level in our UK analysis , thus we estimate that around 50% of patients will have high Th17 proportions. As patients are randomised 1:1 to the different treatments, this should result in around 106 patients randomised to each biomarker-treatment combination (namely Th17 high plus TNF inhibitor, Th17 high plus IL-17A inhibitor, Th17 low plus TNF inhibitor, Th17 low plus IL-17A inhibitor). This sample size also includes a loss-to-follow-up of 10%. The power for different effects of biomarker and treatment are given in the table, where the power for the first row is equivalent to the 2-sided error rate. The rest of the table shows the power for varying degrees of interaction, with the last 2 rows showing scenarios when there is

a biomarker effect but it is in the same direction for both treatments, i.e. when there is no treatment biomarker interaction.

We have given the power for various scenarios. However, head to head comparisons of the 2 drugs have shown no efficacy difference, with a response rate of around 50% for both drugs. We are therefore not interested in a treatment effect per se, it is the interaction between these 2 drugs and the biomarker that will have the potential to personalise treatment that is the aim of this trial. Given that we see no difference in treatment effect in head to head comparisons, an increase in response for patients with high Th17 treated with IL17Ai would presumably imply an increase in response for patients with low TH17 treated with TNFi. Increasing response rates in both these scenarios to 60% would be important, and this we are powered to detect 98% of the time. We are also able to detect a smaller increase in response rate of five percent 84% of the time.

Although we have lower power to detect an increase in response rate in only one of the arms, it is the interaction that is our primary focus and this we are powered to detect. We will incorporate an interim review of the data by the independent DSMC to ensure that the assumed response rates overall are as expected.

Probability of respons	Power (%)	
IL-17Ai	TNFi	
0.5/0.5	0.5/0.5	4.86
0.4/0.6	0.5/0.5	50.14
0.4/0.6	0.55/0.45	83.68
0.4/0.6	0.6/0.4	98.06
0.4/0.6	0.45/0.55	16.24
0.4/0.6	0.4/0.6	5.19

Based on a sample size of 388 and 10,000 simulations

A recently published open-label head to head study of a TNF inhibitor versus an IL-17A inhibitor reported a slightly lower response rate (48 vs 35%)²⁶. We expect a higher achievement of MDA in our study as our patients will have lower baseline active joint counts and psoriasis severity compared to those recruited into this large pharmaceutical sponsored RCT. However even if our response rates are lower (30% vs 50%, rather than 40% vs 60%) our sample size is sufficient to maintain a 95% confidence level and 80% power.

A difference of 20% in rates of achievement of MDA has been chosen as a level that is highly likely to change clinical practice. The Tight Control of PsA (TICOPA) study looking at a treat-to-target approach also used the same predicted difference of 20% although with a lower level of response defined by ACR20. The primary outcome of this study was achieved by 62% of the tight control patients vs 44% of those in standard care. As a result of this study, the first recommendation of the EULAR PsA treatment recommendations is that patients should be treated using a treat-to-target approach and there have been subsequent specific treat-to-target recommendations based on this data alone. We feel that a difference of 20% has the ability to strongly inform changes in practice, particularly as the outcome used in this study is a stringent response equivalent to an optimal treatment goal.

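### The 84% power given for a five-point increase belongs to a scenario that keeps a ten-point increase on IL-17Ai; for five points on both drugs the power is about 50%

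*Protocol*

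**What the plan says.** Protocol section 11.3 powers the trial for the interaction between Th17 status and treatment. It states that "this study sample size has 98% power and 5% (2-sided) significance to detect a biomarker-treatment interaction", with MDA rates of 60%/40% (low/high Th17) on TNFi and 40%/60% on IL-17Ai, around an overall rate of about 50%.

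After arguing that a gain for Th17-high patients on IL-17Ai would go with a gain for Th17-low patients on TNFi, the section says: "Increasing response rates in both these scenarios to 60% would be important, and this we are powered to detect 98% of the time". The next sentence is: "We are also able to detect a smaller increase in response rate of five percent 84% of the time".

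The table that follows, based on 388 participants and 10,000 simulations, lists IL-17Ai rates, TNFi rates and power. The two relevant rows are "0.4/0.6 0.6/0.4 98.06" and "0.4/0.6 0.55/0.45 83.68". No row has a five-point change on both drugs, and none has a five-point change on one drug with the other flat.

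**The concern.** Read in order, the two sentences describe one effect at two sizes. The first is a rise in both favourable groups from about 50% to 60%, which is ten points. The second is a smaller rise of five. Nothing in the second sentence limits it to one drug or says that the other keeps its ten points.

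The row behind the 84% is a different scenario. Its IL-17Ai entry is still 0.4/0.6, so Th17-high patients on IL-17Ai still gain ten points, and only the TNFi gain falls to five.

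This is the one place where the prose gives a power for an effect smaller than the design target on the primary test. If the interaction is not significant, a reader relying on it would take five-point gains to have been tested with 84% power and would regard them as largely excluded.

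**Working it through.** **Inputs, from Protocol sections 11.2 and 11.3.** Logistic regression with a Th17-by-treatment interaction; two-sided 5%; 1:1 allocation; Th17 high/low split 50:50; 388 participants for the table, so 388/4 = 97 per cell. Rates are written low/high Th17, as in the design assumption. Centre and psoriasis severity are left out because the protocol gives no effect sizes for them.

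**Formula.** With d the difference between the two drugs in the log odds ratio for high v low Th17, and SE = √Σ[1/(97·p(1−p))] over the four cells, z = |d|/SE and power = Φ(z − 1.96) + Φ(−z − 1.96).

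**Step 1: the plan's own table.**

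| IL-17Ai | TNFi | Stated % | Formula % | Simulation % |
|---|---|---|---|---|
| 0.5/0.5 | 0.5/0.5 | 4.86 | 5.0 | 4.8 |
| 0.4/0.6 | 0.5/0.5 | 50.14 | 50.7 | 49.9 |
| 0.4/0.6 | 0.55/0.45 | 83.68 | 83.8 | 83.8 |
| 0.4/0.6 | 0.6/0.4 | 98.06 | 97.5 | 97.7 |
| 0.4/0.6 | 0.45/0.55 | 16.24 | 16.9 | 16.8 |
| 0.4/0.6 | 0.4/0.6 | 5.19 | 5.0 | 5.0 |

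(200,000 simulations per row, equal cells.) Every row reproduces to within 0.7 points, so the table is sound and the method matches it. For the 83.68% row: d = 0.811 + 0.401 = 1.212, SE = 0.411, z = 2.95, power 83.8%.

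**Step 2: the effect the sentence describes.**

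- Five points on both drugs (0.45/0.55 with 0.55/0.45): d = 0.401 + 0.401 = 0.803; SE = √(4/(97 × 0.2475)) = 0.408; z = 1.97; power 50.3% (simulation 49.7% with equal cells, 50.4% with random cell sizes).
- Five points on one drug, the other flat (0.45/0.55 with 0.5/0.5): d = 0.401; SE = 0.407; z = 0.99; power 16.7% (simulation 16.0% to 16.6%).
- Five points up in the favourable cells with no mirrored fall (0.50/0.55 with 0.55/0.50): 16.7%.

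**Step 3: what symmetric effect has 84% power.** A mirrored 7.5 points (0.425/0.575 with 0.575/0.425): d = 1.209; SE = 0.411; z = 2.94; power 83.7%.

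**Step 4: can another convention rescue the sentence?** For five points on both drugs, the risk-difference scale gives 50.8%. All 424 evaluable gives 53.8%, and 380 evaluable gives 49.5%. None comes near 84%. Matching the stated 83.68% at five points would need z = 2.94, or about 388 × (2.94/1.97)² ≈ 870 evaluable participants.

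**Cross-check without software.** Five points on both drugs gives a contrast of 10 + 10 = 20 percentage points. The table's second row (0.4/0.6 with 0.5/0.5) gives 20 + 0 = 20 points and is printed at 50.14%. The protocol's own table therefore already implies about 50%.

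**The case against.** The strongest defence is that no printed number is wrong. The 83.68% is correct for its row, that row stands just below the sentence, and it differs from the 98.06% row only in the TNFi rates. The authors probably meant that the TNFi gain alone falls to five points, and on that reading 84% is right. That explains how the figure arose, but the sentence does not state the condition, and it follows directly on one about a rise in both groups.

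A second point is that the next paragraph concedes lower power when only one arm improves, and the table shows about 50% even for a ten-point gain on one drug. This has force against the one-drug figure, which is therefore secondary here. It does not answer the two-drug reading.

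Third, nothing operational hangs on the sentence. The sample size rests on the 20-point difference, the interim review looks at overall response rates, and section 11.2 requires confidence intervals for the four strata, which will show the imprecision. All of that is true, and it limits the damage to interpretation. It does not make the stated power correct.

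**Conclusion.** The sentence is wrong as written. On its plain reading, five points in both favourable groups with mirrored falls in the others, power is about 50% and not 84%. For one drug alone it is about 17%. The trial would miss the symmetric five-point effect about half the time.

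This rests on 388 evaluable participants in equal cells, a 50% average response, the two-sided 5% interaction test and no covariate effects. It is stable across the sample sizes and scales tried (49.5% to 53.8%). If the five points come without a fall in the opposite Th17 group, power is lower still.

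The error lies in the description only. The table, the 98% power for the design effect and the target of 424 all stand.

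**What to change.** In section 11.3, replace the sentence with wording such as: *Power is 84% if MDA rises by ten points in Th17-high patients on IL-17Ai and by five points in Th17-low patients on TNFi, with mirrored falls in the other two groups. For five-point rises on both drugs it is about 50%.* Add a table row for IL-17Ai 0.45/0.55 with TNFi 0.55/0.45, using the same simulation code as the other rows.

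Two optional additions would help the reader: that a mirrored rise of about 7.5 points has 84% power, and that a five-point rise on one drug alone has about 17%.

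The cost is one sentence and one table row. A stated figure becomes less favourable, but no more patients are needed and neither the sample size nor the analysis changes.
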